7.2.2 Administration and Dosage

Appropriately trained personnel will provide instruction pertaining to and supervise the administration of bomedemstat on any day it is taken in the clinic. With the exception of PK sampling collection days (Day 1, Week 2 [Day 15] and another selected regularly scheduled study visit between Week 4 [Day 29] to Week 8 [Day 57]), it is not required that bomedemstat be taken in the clinic; this will be determined based on the patient's regular daily dosing time. On PK sampling collection days, bomedemstat is to be administered in the clinic following an overnight fast (at least 8 hours). Fasting should continue until 1 hour post-dose; water *ad libitum* is permitted during this time. When applicable, the date and time of each administration in the clinic will be recorded in the source notes.

Patients should be instructed:

- That bomedemstat may be taken with or without food.
- To take their bomedemstat QD, at approximately the same time. Though it is suggested that patients dose at night before bed, patients may dose at any time of day that is convenient and mindful of the fasting requirements.
- To swallow their bomedemstat capsules whole, with a glass of water.

All patients will begin dosing on Day 1 at the starting dose of 40 mg/d and be treated daily for 52 weeks. Through the use of dose titration, the dose of bomedemstat will be adjusted for each patient to that dose that provides sufficient exposure to safely inhibit the activity of LSD1 in hematopoietic cells for a fraction of the dosing cycle without resulting in Grade ≥ 1 thrombocytopenia. Given the short lifespan of a human platelet compared to a red cell, approximately 7 days *versus* approximately 120 days, patients will be dosed using the platelet count as a biomarker of the activity of bomedemstat on the inhibition of LSD1. Details on the selection and rationale for the starting dose and titration schedule can be found in Section 3.7. Dose-titration, both upward and downward, is contingent on a hematology assessment. The first up-titration is not permitted before Week 6, and the second up-titration may occur no sooner than 6 weeks after the first up-titration (*e.g.*, if an up-titration occurs at Week 6, the next up-titration may not occur until Week 12). Beginning at Week 16, up-titrations are permitted no more frequently than every 4 weeks from the previous up- or down-titration. Down-titrations can be made (or the current dose maintained) at any time in the best interest of the patient. Up-titrations will be made in increments of 5 or 10 mg/d, and down-titrations in decrements of 10 mg/day.

The hematocrit titration target expected to be associated with a clinically significant therapeutic effect is:

- A hematocrit <42%

Titration and re-challenge rules to be used for titration assessment purposes, based on evaluation of platelet, ANC and hematocrit (Hct) counts are noted below.

Table 1: Titration and Re-challenge Rules

Bomedemstat Titration and Re-challenge Rules				
Important: ANC $\geq 0.5 \times 10^9/L$ (500 neutrophils/ μL) is needed for up-titration. For ANC below this threshold, maintain or adjust the current dose in accordance with the rules below.				
Hematology Assessment		Titration and Re-challenge Rules		
Plt Count ($\times 10^9/L$)	Hct %	Titration?	Titration Rule	Re-challenge Rule [¥]
≥ 450	N/A	Up-titrate [¤]	Increase by 10 mg/d [¤]	N/A
150 – <450	42% – 45%	Up-titrate [¤]	Increase by 5 mg/d [¤]	N/A
150 – <450	<42%	Maintain dose	N/A	N/A
50 – <150	N/A	Down-titrate	Decrease by 10 mg/d	N/A
<50	N/A	HOLD DOSE	N/A	At 50% of prior dose** when platelets return to ≥ 100
ANC, absolute neutrophil count; CBC, complete blood count; Hct, hematocrit; N/A, not applicable; Plt, platelet. [¤] The first up-titration is not permitted before Week 6, and the second up-titration may occur no sooner than 6 weeks after the first up-titration (e.g., if an up-titration occurs at Week 6, the next up-titration may not occur until Week 12). Beginning at Week 16, up-titrations are permitted no more frequently than every 4 weeks from the previous up- or down-titration. Down-titrations can be made (or the current dose maintained) at any time in the best interest of the patient. ^{**} Patients requiring a dose hold should have CBC with differential monitored at least weekly for safety and to enable re-challenge as soon as platelet counts return to $\geq 100 \times 10^9/L$, if safe to do so. Re-challenge at 50% of the previous mg/d dose. [¥] Upon re-challenge, all of the above rules reapply.				

If needed, please consult the Medical Monitor regarding dose modifications of bomedemstat should an AE requiring a dose reduction occur and for the management of clinically significant changes in platelets, neutrophil counts, or other hematologic parameters.

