 - Remind the subject to fast overnight (at least 8 hours) and that bomedemstat will be administered in the clinic

Pharmacokinetics: The PK analysis consists of three sessions of sparse sampling:

- Session 1: Day 1 of dosing
- Session 2: Week 2 (Day 15)
- Session 3: Any regularly scheduled study visit from Week 4 (Day 29) to Week 8 (Day 57)

Each PK sample time-point requires approximately 4 mL of blood, and at each session, 5 samples will be drawn for a total of 20 mL of blood. The required sampling times at each session are:

- Pre-dose (-60 minutes)
- 1h (± 15 minutes) post-dose
- 2h (± 30 minutes) post-dose
- 4h (± 30 minutes) post-dose
- 6h (± 60 minutes) post-dose

Genomic analysis:

- Germline samples (cheek swab and hair roots) may be collected at any time during Screening, up to and including pre-dose Day 1. Repeat sampling may be necessary, pending sample viability and yield.
- Blood samples will be collected pre-dose Day 1, Weeks 12, 24, and 36, every 12 weeks thereafter as long as the patient qualifies for treatment, upon suspicion of disease progression, at EoT and EoS/ED visits.

Future Correlative Studies: Blood samples will be collected for potential future studies pre-dose Day 1, Weeks 12, 24, and 36, every 12 weeks thereafter as long as the patient qualifies for treatment, upon suspicion of disease progression, at EoT and EoS/ED visits.

Cytokines: Blood samples will be collected pre-dose Day 1, Weeks 12, 24, and 36, every 12 weeks thereafter for as long as the patient qualifies for treatment, upon suspicion of disease progression, and at the EoT and EoS/ED visits.

Titration Assessment: At every visit following Day 1, patients will be assessed for dose titrations using the titration and re-challenge rules in [Table 1](#).

- The first up-titration is not permitted before Week 6, and the second up-titration may occur no sooner than 6 weeks after the first up-titration (*e.g.*, if an up-titration occurs at Week 6, the next up-titration may not occur until Week 12). Beginning at Week 16, up-titrations are permitted no more frequently than every 4 weeks from the previous

up- or down-titration. Down-titrations can be made (or the current dose maintained) at any time in the best interest of the patient.

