PV is a trilineage disease in which the production of red cells, granulocytes and megakaryocytes are typically increased above normal levels. Platelet counts at the time of diagnosis are often elevated (mean $720 \times 10^9/L$ [720 k/ μ L]) significantly above the normal range ($>450 \times 10^9/L$ [450 k/ μ L]), though lower than mean platelet counts in patients with ET (Kiladjian *et al.*, 2008). Accordingly, to enable PV patients to reach the optimum dose sufficient to reduce platelets below $450 \times 10^9/L$ (450 k/ μ L) and the hematocrit below 45% while still maintaining an adequate safety margin, a bomedemstat starting dose of 40 mg QD has been selected. Up- or down-titrations will be 5 or 10 mg (as per Table 1 in Section 7.2.2).

[figure not shown]

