At the doses proposed in this study, the concentration of bomedemstat is sufficient to inhibit the activity of LSD1 in hematopoietic cells for a fraction of the 24-hour dosing period allowing LSD1 activity to return and resume its function in normal hematopoiesis. Chronic daily administration of bomedemstat in rat, dog and humans has been well tolerated. No safety signals have been

observed in the AML/MDS, myelofibrosis or ET studies with bomedemstat at doses up to 6 mg/kg/d (360 mg/d for a 60 kg person).

In summary, the starting dose of 40 mg with titration adjustments of ± 5 -10 mg has been chosen for this trial based on the safety, efficacy, and PK observed in clinical trials of bomedemstat in patients with ET and other MPNs. Given that platelet count is a marker of both safety and efficacy in the treatment of MPNs, and that PK data has demonstrated that body mass does not affect the clearance of bomedemstat, data suggests that the majority of patients enrolled will receive optimum clinical benefit at a steady-state dose of 40 mg \pm 10 mg with manageable toxicity.

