6.4 Guidelines

Patient safety is paramount. The guidelines provided below are intended to provide some consistency across sites by providing guidance to be used by the Investigator, the study staff and the patient to safeguard patient safety while maintaining data integrity. The guidelines are not

intended to supersede best clinical judgment by the Investigator. Please contact the Medical Monitor with questions or with planned/known divergences from these guidelines.

1. In general, supportive care (transfusions, administration of anti-microbials, etc.) should be maintained in accordance with institutional policy. Additionally, it is advised that:
 - a. Patients with a platelet count $\leq 10 \times 10^9/L$ (10,000/ μL) be transfused.
 - b. Patients with a hemoglobin (Hb) < 8 g/dL be transfused.
 - c. Phlebotomy be performed to maintain a hematocrit $< 45\%$.
2. Patients taking medications with the potential to induce or inhibit CYP3A4 should be monitored closely for potential effects of co-administration. The Investigator may consider more frequent monitoring of complete blood count (CBC) if clinically indicated. Strong inhibitors and inducers of CYP3A4 are prohibited while on study treatment (Appendix 16.7).
3. Cessation of bomedemstat is invariably associated with a rebound in thrombopoiesis and platelet counts may easily exceed the baseline value. When bomedemstat is discontinued, the platelet count and hematocrit should be monitored closely and an alternative cyto-reductive therapy to lower platelets and hematocrit may commence within 24-48 hours, if appropriate.

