The intended dosing plan for PV patients is predicated on the observation that inhibition of LSD1 has a therapeutic effect when LSD1 is inhibited for a fraction of the 24-hour dosing cycle, sufficient to reduce the production of red cells whose over-production characterizes this condition. The concentrations of bomedemstat needed to achieve maximal effects on growth, differentiation and apoptosis *in vitro* with primary patient-derived malignant myeloid cells as well as *JAK2^{V617F}* cell lines are similar to concentrations that *in vivo* inhibit red cell, platelet and granulocyte production. It is therefore expected that PV patients will require treatment at doses sufficient to reduce platelet counts and hematocrit. These reversible cytopenias can be managed clinically as needed with transfusions as well as broad-spectrum antibiotics in the case of febrile neutropenia, as are already standard practices in the routine management of malignant myeloid diseases.

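### Table 1 gives no dose action for hematocrit above 45% when platelets are 150 to <450, although the titration target is below 42%

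*Combined protocol and SAP*

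**What the plan says.** Section 7.2.2 sets a hematocrit titration target of below 42% and gives the dose rules in Table 1: "Titration and re-challenge rules to be used for titration assessment purposes, based on evaluation of platelet, ANC and hematocrit (Hct) counts are noted below". The Synopsis repeats the table. Its Titration Assessment paragraph says that at every visit after Day 1 "patients will be assessed for dose titrations using the titration and re-challenge rules in" Table 1.

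The surrounding text allows upward steps of 5 or 10 mg/d and downward steps of 10 mg/d. No up-titration is allowed before Week 6, and "the second up-titration may occur no sooner than 6 weeks after the first up-titration". It also says: "Down-titrations can be made (or the current dose maintained) at any time in the best interest of the patient".

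The intent is stated elsewhere. Section 3.7.1 explains the 40 mg starting dose as a way to bring platelets below 450 × 10⁹/L "and the hematocrit below 45% while still maintaining an adequate safety margin". Section 8.2.1 adds: "It is therefore expected that PV patients will require treatment at doses sufficient to reduce platelet counts and hematocrit".

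**The concern.** A titration table should give an action for every state a patient can be in. This one does so everywhere except where platelets are 150 to <450 and hematocrit is above 45%. Its upper bound of 45% conflicts with its own target: being slightly above target triggers an increase, while being well above it triggers nothing.

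The omitted patients are those for whom a hematocrit-driven increase is most clearly meant. The primary efficacy endpoint (Section 12.5) needs hematocrit below 45% for 12 weeks without phlebotomy by Week 36, and a patient above 45% is not meeting it at that visit. With about 20 patients over about 15 sites, an unwritten action and an open step invite site-to-site differences in dosing.

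**Working it through.** No sample-size or error-rate figure bears on this. The check is whether the rows of Table 1 cover every combination of platelets and hematocrit.

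**Inputs** (Section 7.2.2, Table 1; identical in the Synopsis):

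| Platelets (× 10⁹/L) | Hematocrit | Action |
|---|---|---|
| ≥450 | any | +10 mg/d |
| 150 to <450 | 42%–45% | +5 mg/d |
| 150 to <450 | <42% | no change |
| 50 to <150 | any | −10 mg/d |
| <50 | any | hold |

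**Coverage by logic.** The platelet bands join without gaps. Four rows span three of the four bands or state a lower hematocrit limit, but only the 150 to <450 band depends on hematocrit. There the two rows together cover hematocrit <42% and 42%–45%, that is, everything up to 45%. What remains is hematocrit >45%.

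**Coverage on a grid.** Platelets from 0 to 1000 in steps of 10 give 101 values. Hematocrit from 30.0% to 60.0% in steps of 0.1 gives 301. That makes 101 × 301 = 30,401 combinations.
- Table as written: the combinations with no action are platelets 150 to 440 (30 values) with hematocrit 45.1% to 60.0% (150 values), 30 × 150 = 4,500. None matches two rows.
- Cell changed to ≥42%: 0 without an action, 0 matching two rows.

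The 4,500 describes the grid and is not a forecast of patients.

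**Spot checks** (platelets/hematocrit): 300/41 no change; 300/45 +5; 300/46 no rule; 460/46 +10; 140/46 −10.

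**Does other text fill the gap?** The table's footnotes cover timing, dose holds and re-challenge. The text on step sizes allows 5 or 10 mg/d without saying which applies here. Consulting the Medical Monitor (Section 7.2.2) is optional, and Safety Advisory Board review (Section 8.1) is at least quarterly; neither gives an action for the visit.

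**Can patients be in this state?** Entry needs platelets ≥250 × 10⁹/L (Section 6.1.1), and neither list of entry criteria sets a hematocrit ceiling, so a patient can enter in the affected band. Section 3.6 describes platelet production as more sensitive to the drug than red-cell production, and Section 7.2.2 gives lifespans of about 7 and 120 days. Platelets below 450 with hematocrit still above 45% is therefore a plausible early state.

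**Size of the open step.** A 5 mg step is 5/40 = 12.5% of the starting dose, and a 10 mg step is 10/40 = 25%. The closing summary of Section 3.7 expects that "the majority of patients enrolled will receive optimum clinical benefit at a steady-state dose of 40 mg" ± 10 mg. The choice is therefore between half (5/10) and all (10/10) of that upward range.

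**The case against.** The best reply is that nobody would misread the table. The target and the dose rationale both point to an increase, 5 mg/d is the only upward step written for this platelet band, and the Medical Monitor can be asked about hematologic parameters. Section 6.4 also advises "Phlebotomy be performed to maintain a hematocrit" below 45%, so values that stay above 45% should be less common. Most of this stands and keeps the point minor. It does not supply the missing row.

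Three stronger readings are tempting, and the documents do not support them.

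- *The gap lets a site leave the dose unchanged.* The freedom to maintain the dose is tied to the patient's best interest and applies to every row, including 42%–45%. It does not come from the gap and would survive the fix. Only the missing default action and step come from the gap.
- *A visit in the gap costs weeks of effective dosing.* The spacing rule runs from up-titrations actually made, so a missed first step can be taken at the next visit. One can construct a patient above 45% at Week 6 only, and at 42%–45% otherwise, who reaches 50 mg at Week 14 or 16 instead of Week 12. That needs this exact history and a site that reads the blank as an instruction not to increase. Even then, Week 16 is eight weeks before Week 24 (36 − 12), the last start of a 12-week run ending by Week 36.
- *The table is also wrong to hold the dose when phlebotomy has brought hematocrit below 42%.* Holding there is a defensible cautious rule. The platelet count is the stated dosing biomarker, Section 3.6 names severe thrombocytopenia as the greatest clinical risk, and the decision is reviewed at every visit.

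**Conclusion.** The point holds as a gap in the dosing table: in both visible copies, platelets of 150 to <450 with hematocrit above 45% have no default action and no stated step. The endpoint and its analysis are not in question.

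The importance is minor. The documents do not show how many patients would be in this state or how sites would act, so no effect on the Week 36 response rate can be derived. One patient is 1/20 = 5 percentage points of a 20-patient rate, but that is true of any issue in this trial and is not an estimate of harm.

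The conclusion rests on the visible text. Part of the Section 3.7 titration rationale was not in the text reviewed, and a block in the Synopsis dosing section is redacted. Either could hold guidance that could not be checked, although the two visible tables would still need correcting.

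**What to change.** In Table 1 and in the Synopsis copy, change the hematocrit cell of the up-titration row for platelets 150 to <450 from 42%–45% to ≥42%, keeping +5 mg/d. If the sponsor intends a different step above 45%, add a separate row for it. The neutrophil condition, the spacing of up-titrations and the platelet-based reductions stay as they are.

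The cost is one table cell in two places, made by amendment, with the medical team confirming the step. Endpoint, visit timing and analysis do not change.

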7.2.2.1 Provisional Dose(s); Unacceptable Toxicity at the Starting Dose (D_s)

Although unlikely, it is possible that unacceptable toxicity may be seen at the D_s (40 mg/d); the D_s could also be the maximum tolerated dose (MTD). To address this possibility, contingencies are needed. If the SAB determines the D_s is too high, then the enrollment of additional patients at lower doses will be necessary. If required, the D_s will be reduced first to 35, and subsequently to 30 mg/d.

7.2.2.2 Missed Doses

Patients who do not take their bomedemstat dose at the usual time should take it immediately upon noting it was not taken; the patient should not take the dose more than 12 hours after the usual dosing time. If a patient misses a dose, they should not take two doses the following day, but should notify study personnel and continue with their normal daily dose the following day. If vomiting occurs within 30 minutes after taking bomedemstat and all expelled capsules remain intact, another dose may be taken. For a dosing hiatus due to an SAE, the Medical Monitor may be consulted for guidance on re-start of dosing. Patients who miss an extended duration of bomedemstat doses or exhibit serial non-compliance may be removed from the study at the discretion of the Sponsor.

7.2.2.3 Interruption of Dosing

Patients requiring a dose hold according to the Titration and Rechallenge Rules, or due to an (S)AE, should be monitored at least weekly for safety purposes and to enable re-challenge as soon as platelet counts return to the required level, if it is safe to do so. During these visits, patients are required to undergo CBCs with differential only.

8 SAFETY ADVISORY BOARD (SAB) REVIEWS AND MANAGEMENT OF STUDY TOXICITIES

8.1 Safety Advisory Board (SAB) Reviews

Safety will be monitored throughout the study in accordance with a Safety Advisory Board Plan (SABP) by a SAB made up of MPN clinical trials specialists with extensive clinical experience. The SAB will provide recommendations regarding study conduct and guidance to Investigators to ensure the safety and well-being of study patients. To do so, the SAB will review safety parameters and PD markers at least quarterly. Expedited, *ad hoc* reviews may also occur when:

- Fatal or life-threatening reaction assessed as related to bomedemstat (possibly, probably or definitely), regardless of expectedness, is reported
 - A CIOMS/MedWatch form for all expedited (serious, unexpected, related) SAEs will be sent to the SAB for review.
- Occurrence of other safety-related issues such as an event meeting any of the Stopping Rules as *per* Section 8.2.3, or evidence of unexpectedly severe effects on hematopoiesis which pose a medical concern and may necessitate bomedemstat dose adjustment or discontinuation.

In the event an expedited, *ad hoc* safety review is warranted, Sponsor will immediately notify the SAB, provide preliminary information regarding the event(s), and request that a SAB review be scheduled. No later than 2 business days after Sponsor notification of the event(s), Sponsor will provide the SAB with all relevant and available data.

SAB responsibilities will remain in effect until the study has ended.

8.2 Management of Study Toxicities

AE severity will be evaluated using the National Cancer Institute (NCI) Common Terminology Criteria for Adverse Events (CTCAE) version 5, published 27-NOV-2017.

Stopping rules are defined in Section 8.2.3 below. Expected bomedemstat toxicities based on non-clinical and clinical studies are reported in the latest available edition of the IB.

8.2.1 Hematologic Toxicity

Hematologic values outside of the normal reference range are inherent features of MPNs and are expected effects of many therapeutic attempts to manage these diseases. The effects of bomedemstat on normal myeloid hematopoiesis observed in non-clinical and clinical studies are expected; these are PD effects of LSDi by bomedemstat, thus are considered on-target effects.

Both genetic knockdown (KD) of LSD1 mRNA and pharmacologic inhibition of LSD1 show that the loss of LSD1 activity arrests the production of mature red cells, platelets, and granulocytes while over-producing monocytes (Sprussel *et al.*, 2012; Kerenyi *et al.*, 2013). Production of cells of lymphoid lineage, B and T cells, is unimpaired indicating that LSD1 has very cell-specific functions and its inhibition also has very specific effects. LSDi in malignant myeloid cells causes the induction of monocytic differentiation markers, as well as a reduction of self-renewal

potential of neoplastic cells, all of which eventually result in apoptosis of treated cells. Thus, the anemia, thrombocytopenia, neutropenia and monocytosis attending LSDi reflect primary PD effects. The kinetics of anemia, thrombocytopenia, and neutropenia following complete LSDi are a function of the lifespan of the individually affected cell types. Over the course of LSDi, platelet and neutrophil counts are the most affected, reflecting their short mean lifespans of approximately seven and twelve days, respectively. Recovery of peripheral counts is reversible, rapid, and temporarily overshoots baseline hematologic values. At lower doses, the effects on hematopoiesis are much less pronounced suggesting that a modicum of residual LSD1 activity is sufficient to support blood cell formation. Thus, both the duration of LSDi as well as the degree of inhibition are critical to the PD effects on myeloid lineages.

The intended dosing plan for PV patients is predicated on the observation that inhibition of LSD1 has a therapeutic effect when LSD1 is inhibited for a fraction of the 24-hour dosing cycle, sufficient to reduce the production of red cells whose over-production characterizes this condition. The concentrations of bomedemstat needed to achieve maximal effects on growth, differentiation and apoptosis *in vitro* with primary patient-derived malignant myeloid cells as well as *JAK2^{V617F}* cell lines are similar to concentrations that *in vivo* inhibit red cell, platelet and granulocyte production. It is therefore expected that PV patients will require treatment at doses sufficient to reduce platelet counts and hematocrit. These reversible cytopenias can be managed clinically as needed with transfusions as well as broad-spectrum antibiotics in the case of febrile neutropenia, as are already standard practices in the routine management of malignant myeloid diseases.

